9.1.2 Treatment of Outliers

Individual plasma concentrations, if deemed to be anomalous, may be excluded from the analysis at the discretion of the pharmacokineticist following a review of available documentation (eg, bioanalytical report, clinical report) and communication with the sponsor. Any such exclusion will be clearly listed in the study report along with justification for exclusion.

Entire plasma concentration-time profiles for a patient may be excluded following review of available documentation (eg, bioanalytical report, clinical report) and communication with the sponsor. Any such exclusion will be clearly listed in the study report along with justification for exclusion.

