#### **3.2 Investigational Device Background**

The FAST PV and mGFR Technology™ is a direct measurement of PV and GFR that relies on reading the concentration of fluorescent markers attached to different size dextran molecules introduced into the bloodstream. The test is intended as an adjunct to current methods utilized to assess kidney function.

The FAST PV and mGFR Technology includes intravenously (IV) administered fluorescent markers, timed blood draws, a validated fluorometric assay, and a computed algorithm to integrate the results and calculate the GFR.

The FAST PV and mGFR Technology will aid in identifying and determining the extent of renal dysfunction, therefore promoting early treatment, including dialysis initiation, as well as enrollment and stratification for clinical studies. It could also be used to determine the effect of a clinical maneuver on GFR such as volume resuscitation.

CONFIDENTIAL

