Both Iohexol and the FAST mGFR technologies utilized timed blood draws and subsequent concentrations to calculate a predicted total AUC. The dose of marker given was divided by this AUC to calculate the mGFR, with scaling based on body surface area. The FAST mGFR utilized 3 blood draws taken at early time points out to 2 hours. A fourth virtual point was calculated based on the PV at T0 (the starting concentration in the plasma just after the dose is given or time 0). The Iohexol GFR 6 test utilized a blank, plus a minimum of 6 additional blood draws taken over 6 hours to determine the AUC. Iohexol, having a much smaller molecular size, distributes differently within the extracellular space, so some difference in mGFR between the 2 markers was anticipated. FAST BioMedical expected to measure mGFR values slightly lower than Iohexol in normal patients, as most single marker systems like Iohexol have difficulty resolving the early decay phase when the clearance is rapid. It was expected that the FAST mGFR measurements would be within 10% in the lower GFR groups. Prior studies conducted by FAST BioMedical using both the VFI and Iohexol in anesthetized dogs, have shown there were differences between the 2 methods. Analysis of the single marker decay rate showed that it normally resolved to a falsely high volume of distribution making the resulting mGFR biased higher than the FAST 2 marker system, which quantifies the initial volume of marker distribution. This small error in AUC was only significant in mGFRs above 80 mL/min.

In addition to studying a range of GFRs using different measurement techniques, FAST BioMedical intended to evaluate FAST’s measured PV method against a standard clinical estimate of PV, specifically Nadler’s Formula (Nadler et al 1962).

$$\text{Plasma Volume (males)} = 0.3669 \times (\text{Height [m]})^3 + 0.03219 \times (\text{Body Weight [kg]}) + 0.6041$$

$$\text{Plasma Volume (females)} = 0.3561 \times (\text{Height [m]})^3 + 0.03308 \times (\text{Body Weight [kg]}) + 0.1833$$

CONFIDENTIAL

The difference between a measured and estimated PV are between plus 20% to minus 30% ([Feldschuh and Enson, 1977](#)) using radioiodinated human serum albumin as the measured plasma marker. Since Nadler's work was based primarily on measurements in healthy subjects, it was expected there may be a greater range seen with the CKD population in this study.

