**7.7.2 Blinding of Treatment Assignment**

Not applicable. This is an open-label study.

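### SAP 9.1.2 allows discretionary exclusion of concentrations, in contact with the sponsor, without requiring that this be settled before the iohexol result is known

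*SAP*

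**What the plan says.** SAP 9.1.2 opens two routes.

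- **Single values.** Plasma concentrations judged anomalous "may be excluded from the analysis at the discretion of the pharmacokineticist following a review of available documentation" (the bioanalytical and clinical reports are given as examples) "and communication with the sponsor".
- **Whole profiles.** "Entire plasma concentration-time profiles for a patient may be excluded following review of available documentation", again with sponsor communication. Here no decision-maker is named.

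The safeguard is disclosure: "Any such exclusion will be clearly listed in the study report along with justification for exclusion". The section does not define anomalous and sets no point in time by which exclusions must be settled.

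The rule stands under SAP 9.1, Pharmacokinetic Assessments. FAST plasma volume and FAST mGFR are dealt with in SAP 9.2, which has no exclusion rule. SAP 10.1.10.2 compares FAST mGFR with iohexol clearance in Cohorts 2 to 4, using a Pearson correlation with 95% confidence interval and Bland-Altman plots in each cohort. It has no exclusion rule either. Neither document puts exclusions before knowledge of the iohexol result, and neither plans to repeat the comparison without exclusions.

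**The concern.** Agreement between FAST and iohexol is judged from the spread of paired differences. If a FAST input can be dropped after the paired iohexol value is known, a value that agrees badly is more likely to be looked at twice, even in good faith. The spread then shrinks and the correlation rises because of the selection and not because of the method. Listing the exclusions tells the reader that a choice was made, but not what the comparison would have shown without it. The sponsor, whose technology is being assessed, is part of the conversation, so the order of events is worth fixing in writing.

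**Working it through.** **Step 1. Does the rule reach the FAST inputs?** No sentence says so. The inference rests on these places:

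- SAP Tables 1.5 and 1.6 schedule one FD001/FD003 plasma sample under a joint PK/PD column. There is no separate tube for FAST.
- Protocol 3.2 describes FAST as timed draws, an assay and "a computed algorithm to integrate the results and calculate the GFR". The concentrations are its inputs.
- Protocol 8.4.2, the pharmacokinetic parameter section, also prescribes how FD003 residuals are handled for FAST mGFR and plasma volume in Cohort 2.
- SAP 9.2 and 10.1.10 offer no competing rule. If 9.1.2 were confined to pharmacokinetics, FAST inputs would have no exclusion rule at all, and the order of events would still be open.

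A subject whose FD001/FD003 profile is excluded could stay in the PD Evaluable Population through another estimate (SAP 10.1.4). That subject would have no FAST value to pair, and SAP 10.1.1 rules out imputation.

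**Step 2. Number of pairs.** The plan's figure reproduces: 4 cohorts x 8 = 32 subjects (SAP 10.1.12). Only Cohorts 2 to 4 have both methods, so there are at most 3 x 8 = 24 pairs, and at most 8 in each cohort plot.

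**Step 3. Effect of dropping whole subjects.** The SAP does not spell out limits of agreement. I take the usual lines, mean difference ± 1.96 SD. Their width is 3.92 x SD, so the ratio of widths equals the ratio of SDs:

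ratio = SD(after exclusion) / SD(all pairs)

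The simulation used 100,000 replicates of normal differences with true mean 0 and no genuine outlier. In the aware case, the k pairs with the largest absolute difference are dropped. In the unaware case, k pairs are dropped without regard to the difference.

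| Pairs | Dropped | Ratio, aware | Narrowing | Ratio, unaware |
|---|---|---|---|---|
| 8 | 1 | 0.800 | 20% | 0.994 |
| 8 | 2 | 0.656 | 34% | 0.987 |
| 8 | 3 | 0.535 | 46% | 0.974 |
| 24 | 1 | 0.903 | 10% | 0.999 |
| 24 | 2 | 0.832 | 17% | 0.999 |
| 24 | 3 | 0.772 | 23% | 0.998 |

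The last column shows that exclusion as such does little. The narrowing comes from choosing with the difference in view.

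**Step 4. Correlation.** In 40,000 bivariate-normal replicates, dropping the single worst pair of 8 moves the median r from 0.53 to 0.68 (true r 0.5), from 0.73 to 0.83 (true r 0.7) or from 0.91 to 0.95 (true r 0.9). With 24 pairs and true r 0.9 it moves only from 0.90 to 0.92.

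**Step 5. Dropping one concentration instead of a subject.** As a stand-in for the algorithm, I used a log-linear slope on the 15, 30, 60 and 120 minute samples (20,000 replicates; assumed rate 0.010 per minute, concentration CV 3 to 10%, iohexol error 5 to 10%). One point is removed in each of the 3 worst-agreeing of 24 subjects, wherever that brings FAST closer to iohexol. The ratio is 0.854 to 0.912, a narrowing of about 9 to 15%.

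**The case against.** The strongest objections, and what stands of each:

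- **The rule is written for pharmacokinetics.** True. Its reach to FAST is inferred, though Step 1 supports the inference well.
- **Open-label status.** A reader might infer from the Protocol 7.7.2 entry, "Not applicable. This is an open-label study", that the analyst sees the iohexol answer. It does not show that. The entry concerns treatment assignment, and every subject in Cohorts 2 to 4 is planned to receive both agents, so knowing the treatment reveals nothing about the iohexol GFR. The assays are also different: fluorometric for FD001/FD003, chromatographic for iohexol. The documents are silent on who sees what and when. They show an opportunity, not that it will be used, and nothing suggests intent.
- **All comparators should be masked.** This cannot be done. The CKD-EPI eGFR decides eligibility and cohort, and Nadler's inputs (height, weight, hematocrit) are collected at screening. Only the iohexol result can be kept apart.
- **Every aspect of agreement would improve.** Not so. If the value furthest from the sample mean is dropped, the ratio for 1 of 8 is 0.77, but the average absolute mean difference grows by about 22%. The effect is on spread and correlation, not reliably on mean bias.
- **The comparison is secondary and descriptive.** Correct (Protocol 3.7 and 10.3.2). There is no test, margin or pass/fail decision, so no type I error is at stake. Equally, the plots and coefficients are then the result itself.
- **Individual data are listed.** SAP section 11 lists concentrations, PD parameters and reasons for exclusion. That is real transparency. However, neither document gives the FAST algorithm in full for this study, so a reader could not readily rebuild an excluded FAST value from the listings.
- **Three Phase 2a draws against four early samples here.** Protocol 3.4.3 reports that "The FAST mGFR utilized 3 blood draws taken at early time points out to 2 hours". Which samples enter the calculation now is a question of algorithm specification and is separate from the outlier rule.

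**Conclusion.** The concern holds in a limited form. SAP 9.1.2 leaves exclusions to judgement, in contact with the sponsor, without a criterion or a required order relative to the iohexol result. By inference this covers the FAST side of a secondary, descriptive comparison.

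In the worst case, limits of agreement narrow by about 20% for 1 of 8 subjects, 10% for 1 of 24 and 17% for 2 of 24, against about 0 to 1% when those exclusions ignore the difference. These figures assume normal differences and removal of exactly the worst-agreeing whole subjects. The documents give no SD of differences and no expected number of exclusions, so the figures show what the rule permits and do not forecast what will happen.

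A reader might go further and conclude that the agreement results will be biased or that the sponsor will steer them. The documents do not support that: they require each exclusion to be justified and listed, and they do not say that iohexol values are in view when the decision is made.

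**What to change.** Add to SAP 9.1.2:

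1. A statement of whether the section applies to FAST inputs and to iohexol concentrations. Its wording on individual plasma concentrations is not limited to one marker.
2. All exclusions of FD001/FD003 and of iohexol concentrations, and the resulting FAST and iohexol mGFR values, are documented and locked in a dated file before the two sets of results are merged. Exclusions rest on bioanalytical or clinical documentation recorded before the merge, so that a documented sampling or dosing failure can still be acted on.
3. The correlation and Bland-Altman results are reported both with all available data and with exclusions.

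The lock should be limited to FAST against iohexol, since eGFR and Nadler plasma volume cannot be masked.

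The cost is SAP wording, a dated file, a short delay before the merge and one repeat of the comparison outputs. No new data or visits are needed.

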9.1.3 Non-Quantifiable Concentrations

All concentration values reported as no results (not collected or not determined) values will be treated as missing. For the calculation of concentration summaries and plotting mean and individual concentration time profiles, below the quantifiable limit (BLQ) values will be treated as 0 prior to the first measurable concentration. After the first measurable concentration, subsequent BLQ values are treated as missing.

9.2 Pharmacodynamic Parameters

9.2.1.1 Plasma Volume

Plasma volume will be determined using FAST PV Technology for Cohorts 1 through 4.

Additionally, PV will be estimated using Nadler's formula (Nadler et al 1962) for Cohorts 1 through 4 as follows:

$$PV_{males}[L] = (0.3669 \times (Height[m])^3 + 0.03219 \times (Body\ Weight[kg]) + 0.6041) \times (1 - \text{hematocrit})$$

$$PV_{females}[L] = (0.3561 \times (Height[m])^3 + 0.03308 \times (Body\ Weight[kg]) + 0.1833) \times (1 - \text{hematocrit})$$

9.2.1.2 Glomerular Filtration Rate

Measured GFR will be determined using FAST mGFR Technology for Cohorts 1 through 4.

Glomerular filtration rate will also be determined using the Iohexol clearance test, a widely accepted research gold standard for measuring GFR in patients with stable renal function, for Cohorts 2 through 4. Plasma concentrations of Iohexol will be determined using a validated high performance liquid chromatography assay.

Additionally, eGFR will be calculated using the MDRD (Levey et al 1999), CKD-EPI (Levey et al 2009) and Cockcroft-Gault (Cockcroft et al 1976) equations for Cohorts 1 through 4.

The MDRD equation (Levey et al 1999) is as follows:

$$\text{GFR } [\text{mL/min}/1.73 \text{ m}^2] = 175 \times (\text{S}_{\text{cr}}[\text{mg/dL}])^{-1.154} \times (\text{Age}[yr])^{-0.203} \times (0.742 \text{ if female}) \times (1.212 \text{ if African American})$$

The CKD-EPI equation (Levey et al 2009) for eGFR for specified race, sex, and S_{cr} in mg/dL and $\mu\text{mol/L}$ is presented in below Table 3.1 and Table 3.2, respectively.

The Cockcroft-Gault equation (Botev et al 2009) is as follows:

$$\text{GFR } [\text{mL/min}] = [(140 - \text{Age}[yr]) \times (\text{Weight}[kg]) \times 0.85 \text{ if female}] / (72 \times \text{S}_{\text{Cr}}[\text{mg/dL}])$$

Table 3.1 Chronic Kidney Disease Epidemiology Collaboration Equation for Estimating Glomerular Filtration Rate Expressed for Specified Race, Sex, and Serum Creatinine (mg/dL)

Race	Sex	S _{cr} (mg/dL)	Equation (age in years for ≥ 18)
Black	Female	≤ 0.7	$GFR = 166 \times (S_{cr}/0.7)^{-0.329} \times (0.993)^{Age}$
Black	Female	> 0.7	$GFR = 166 \times (S_{cr}/0.7)^{-1.209} \times (0.993)^{Age}$
Black	Male	≤ 0.9	$GFR = 163 \times (S_{cr}/0.9)^{-0.411} \times (0.993)^{Age}$
Black	Male	> 0.9	$GFR = 163 \times (S_{cr}/0.9)^{-1.209} \times (0.993)^{Age}$
White or other	Female	≤ 0.7	$GFR = 144 \times (S_{cr}/0.7)^{-0.329} \times (0.993)^{Age}$
White or other	Female	> 0.7	$GFR = 144 \times (S_{cr}/0.7)^{-1.209} \times (0.993)^{Age}$
White or other	Male	≤ 0.9	$GFR = 141 \times (S_{cr}/0.9)^{-0.411} \times (0.993)^{Age}$
White or other	Male	> 0.9	$GFR = 141 \times (S_{cr}/0.9)^{-1.209} \times (0.993)^{Age}$

Source: National Institute of Diabetes and Digestive and Kidney Diseases, Estimating Glomerular Filtration Rate (2015)

Table 3.2 Chronic Kidney Disease Epidemiology Collaboration Equation for Estimating Glomerular Filtration Rate Expressed for Specified Race, Sex, and Serum Creatinine (μmol/L)

Race	Sex	S _{cr} (μmol/L)	Equation (age in years for ≥ 18)
Black	Female	≤ 61.9	$GFR = 166 \times (S_{cr}/61.9)^{-0.329} \times (0.993)^{Age}$
Black	Female	> 61.9	$GFR = 166 \times (S_{cr}/61.9)^{-1.209} \times (0.993)^{Age}$
Black	Male	≤ 79.6	$GFR = 163 \times (S_{cr}/79.6)^{-0.411} \times (0.993)^{Age}$
Black	Male	> 79.6	$GFR = 163 \times (S_{cr}/79.6)^{-1.209} \times (0.993)^{Age}$
White or other	Female	≤ 61.9	$GFR = 144 \times (S_{cr}/61.9)^{-0.329} \times (0.993)^{Age}$
White or other	Female	> 61.9	$GFR = 144 \times (S_{cr}/61.9)^{-1.209} \times (0.993)^{Age}$
White or other	Male	≤ 79.6	$GFR = 141 \times (S_{cr}/79.6)^{-0.411} \times (0.993)^{Age}$
White or other	Male	> 79.6	$GFR = 141 \times (S_{cr}/79.6)^{-1.209} \times (0.993)^{Age}$

Source: National Institute of Diabetes and Digestive and Kidney Diseases, Estimating Glomerular Filtration Rate (2015)

10 STATISTICAL METHODS

10.1 General

The statistical analysis will be conducted following the principles specified in the International Council for Harmonisation (ICH) Topic E9 Statistical Principles for Clinical Trials (CPMP/ICH/363/96).

All statistical tabulations and analyses will be done using SAS[®], Version 9.3 or higher.

Unless otherwise noted, continuous variables will be summarized using the number of non-missing observations (n), arithmetic mean (mean), standard deviation (SD), median, minimum, and maximum; categorical variables will be summarized using the frequency count and the percentage of subjects in each category.

Geometric mean and Geometric CV% will be included for PK parameters, where applicable.

In the data listings, study day relative to single dose of IMP will be presented. Study day relative to single dose will be calculated as: event date – single dose date (+ 1 if event date \geq single dose date).

Unless otherwise specified, baseline will be defined as the last non-missing measurement obtained prior day 1 treatment administration.

For safety summaries, the unscheduled and repeat assessments will not be summarized; however, all results will be included in the data listings.

10.1.1 Handling of Dropouts or Missing Data

Missing data will not be imputed.

10.1.2 Multicenter Studies

This is a multi-center study. Cohorts 1 and 2: ICON Early Phase Services, LLC and Cohorts 3 and 4: University of Alabama Birmingham.

10.1.3 Examination of Subgroups

No subgroups planned for this study.

10.1.4 Analysis Populations

Enrolled subjects: Subjects who signed informed consent and met all the criteria as per the protocol.

Pharmacokinetic Full Population: All subjects in Cohorts 2 through 4 who receive a known amount of study drug and have at least one quantifiable concentration of FD001 or FD003 in plasma or FD001 in urine and subjects in Cohort 1 who receive a known amount of study drug and have at least one quantifiable concentration of FD001 in plasma or urine.

Pharmacokinetic Evaluable Population: All subjects in Cohorts 1 through 4 who receive a known amount of study drug and have at least 1 estimable PK parameter.

Safety Population: All subjects who received any amount of study drug.

Pharmacodynamic Evaluable Population: All subjects in Cohorts 1 through 4 who have either a PV or GFR estimate using any of the techniques under study. Subjects in Cohort 1 will not contribute to the overall PD statistical analysis.

10.1.5 Subject Accountability

Summaries of analysis populations and subject disposition will be presented by cohort and overall and will contain the following information:

- Number of subjects screened
- Number of enrolled subjects
- Number and percent of subjects who received VFI
- Number and percent of subjects who received Iohexol
- Number and percent of subjects who received Albumin infusion
- Reason for not receiving VFI/ Iohexol/Infusion
- Number and percent of subjects who completed the study
- Number and percent of subjects who discontinued early from the study and reason for early discontinuation
- Number and percent of subjects in each of the analysis population defined in Section 9.1.4

Subject disposition data and exclusions from the analysis populations will be presented in listings.

10.1.6 Protocol Deviation Reporting

A protocol deviation is defined as any intentional or unintentional change to, or noncompliance with, the approved protocol procedures or requirements. Deviations may result from the action or inaction of the subject, investigator, or site staff.

The impact of each protocol deviation will be assessed. All key protocol deviations that have an impact on the analysis populations defined in Section 9.1.4 will be listed by subject.

10.1.7 Subject Demographics and Baseline Characteristics

10.1.7.1 Subject Demographics Characteristics

Demographics and baseline characteristics summary will be summarized descriptively by cohort and overall based on the Safety Set.

Summary statistics (n, mean, SD, minimum, median, and maximum) will be tabulated for the observed values for all continuous demographic parameters. Frequencies and percentages will be tabulated for categorical data. In addition, listings will also be provided.

10.1.7.2 Medical and Surgical History

Medical history will be coded using the Medical Dictionary for Regulatory Activities (MedDRA, Version 20.0) and listed by subject for the Safety Population.

Medical and surgical history will be listed.

10.1.8 Analysis of Efficacy Data

No efficacy analysis planned for this study.

10.1.9 Analysis of Pharmacokinetic Data

For Cohorts 1 through 4, subject plasma and urine concentration-time profiles will be listed and summarized for each analyte by cohort and nominal sampling time. Summary statistics will be listed and summarized for each PK parameter by cohort and analyte. Only CL_r , A_e , C_{max} , and t_{max} will be computed and summarized for Cohort 1.

The plasma and urine drug concentrations will be summarized descriptively by cohort and nominal time point in tabular. In addition, the plasma and urine concentration-time will be displayed graphically on linear and semi-log scales by cohorts.

Pharmacokinetic parameters for each analyte will be listed and summarized descriptively by treatment using the PK full Population, including n, arithmetic mean, SD, minimum, median, maximum, geometric mean (GM), geometric CV%; geometric CV% calculated as the square root of the exponentiated SD of the natural log transformed data ($SQRT(exp(sln^2)-1)$), where appropriate. For T_{max} , only n, minimum, median, and maximum will be reported.

10.1.10 Analysis of Pharmacodynamic Data

10.1.10.1 Plasma Volume (PV)

The FAST PV Technology plasma volume (PV) will be compared to PV estimated using Nadler's formula. Plasma volume data will be listed and summarized by presenting descriptive statistics of raw data and for change in plasma volume.

Correlation analysis will be done for comparing the PV measured using FAST PV method and PV estimated using Nadler's Formula for each cohorts. Pearson product-moment correlation coefficient, standard error with 95% confidence interval of the coefficient will be provided.

In addition scatter plot will also be provided to support the correlation analysis. Also, histogram will be provided for the magnitude of difference (PV using FAST PV - PV estimated using Nadler's formula).

